12.2.1.2 Secondary outcome variables

The ORRs at 24 weeks will be determined for each treatment, and their difference and 95% CI (derived as for the primary outcome variable) will be presented. Patient without measurable disease at baseline (ie, patients with bone metastases only or with complete remission after prior taxane- or anthracycline-based first line chemotherapy for advanced breast cancer) will not be included in the analysis of ORR.

A comparison of mean E₂ serum concentrations at timepoint(s) post Day 1 will be performed using analysis of covariance (ANCOVA), with treatment group, baseline E₂ serum

concentrations and country as covariates. Least square means and the 95% CI for their difference will be presented.

Further exploratory analyses of efficacy and/or PD outcomes (eg, FSH serum concentrations) may be performed, as deemed appropriate.

Exploratory analyses may investigate whether there is any additional effect of prior chemotherapy for ADVANCED BREAST CANCER use on the efficacy and/or PD outcomes.

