4.2 Exclusion criteria

Subjects should not enter the study if any of the following exclusion criteria are fulfilled.

1. Patients who have received tamoxifen or other hormonal therapies as adjuvant therapy for breast cancer within 24 weeks before randomisation and/or who have received prior treatment with hormonal therapies for advanced breast cancer.
2. Patients who have received LHRHa as adjuvant therapy for breast cancer within 48 weeks before randomisation.
3. Patients who have received any radiotherapy as adjuvant therapy for breast cancer or for advanced breast cancer within 4 weeks before randomisation.
4. Patients who have received any chemotherapy within 4 weeks before randomisation.
5. Patients who have relapsed during adjuvant hormonal therapy or within 48 weeks after completion of adjuvant hormonal therapy and/or patients who have relapsed during adjuvant chemotherapy or within 24 weeks after completion of adjuvant chemotherapy.
6. Patients who have received chemotherapy for advanced breast cancer with the exception of first line chemotherapy providing that a) there is no evidence of progressive disease since the start of the chemotherapy and b) the patient has menses after starting chemotherapy.
7. Patients who have prior treatment with trastuzumab or lapatinib for early breast cancer as adjuvant therapy within 4 weeks before randomisation and/or who have prior treatment with trastuzumab or lapatinib for advanced breast cancer.
8. Presence of life-threatening metastatic visceral disease, defined as extensive hepatic involvement, or any degree (proven or suspected) of brain or leptomeningeal involvement (past or present) or symptomatic pulmonary lymphangitic spread. Patients with discrete pulmonary parenchymal metastases are eligible, provided their respiratory function is not compromised as a result of disease.
9. Estimated survival less than 24 weeks from the start of study therapy (Day 1) based on clinical judgment.

10. History (within previous 3 years before randomisation) of systemic malignancy other than breast cancer with the exception of basal cell/squamous cell carcinoma of the skin or cancer of the cervix that has been satisfactorily controlled.
11. Platelets $<100 \times 10^9/L$; total bilirubin $>1.5 \times$ upper limit of reference range (ULRR); alanine aminotransferase (ALT) or aspartate aminotransferase (AST) $>2.5 \times$ ULRR if no demonstrable liver metastases or $>5 \times$ ULRR in presence of liver metastases.

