6.2 Data collection and enrolment

6.2.1 Screening and demographic measurements

The following screening and demographic data will be collected in the eCRF (see Table 2 for the timing of these assessments). Tests performed before screening may be used as screening assessments with patient informed consent

- Provision of written informed consent
 - Provision of written informed consent must be obtained prior to screening for all patients.
- Date of birth, sex, and race
- Relevant medical and surgical history, including menstrual status and concurrent illness
- Urine pregnancy test
- Previous therapy, including surgery for early breast cancer (concomitant medications will be recorded from the informed consent day until the Study Completion Visit)
- Physical examination
- Bone scan and chest assessment
 - If there are any hotspots detected by bone scan, then they should be evaluated as appropriate according to local practice (eg, by x ray, computed tomography scan, or MRI).
 - Chest assessment must be done by chest X ray or chest CT or chest MRI.
 - See Section 6.3.1 for further details
- Tumour assessment according to RECIST criteria (Ver1.1)
- Haematology, clinical chemistry analysis and sex hormone assessment

- For assessment of patient eligibility for study entry, the blood samples will be collected according to standard local practice and analysed at the local laboratory of each study centre using standard procedures. Platelets, AST, ALT, total bilirubin, E₂, and FSH must be measured. The actual values will not be collected in the eCRF or entered into the study database but confirmation that the values meet the inclusion or exclusion criteria will be recorded in the eCRF.
- Note that the E₂ and FSH assays used by the local laboratories may be different from those used by the central laboratory (Covance Asia Pte. Ltd., see Section 6.3.3).
- Histological or cytological confirmation of breast cancer
- Confirmation of ER, PgR and HER2 status of primary or secondary tumour tissue
- Confirmation that Patients fulfil all inclusion and exclusion criteria before randomised to treatment.
- Confirmation of AEs and concomitant medications

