12.2 Methods of statistical analyses

Formal statistical hypothesis testing will only be performed on the efficacy and PD outcome variables (main study). All confidence intervals (CIs) will be two-sided, 95% intervals. See Section 12.1 for a description of analysis sets used in each analysis.

Summaries presented will include patient inclusion/exclusion, attendance at study visits, baseline and demographic variables, medical history, prior and concomitant medication, and all efficacy and safety endpoints.

Each table, figure and listing will be created for “Japanese centres only”, “Non-Japanese centres only” and for “All centres”

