12.2.1 Analysis of efficacy and pharmacodynamic outcome variables (main study)

12.2.1.1 Primary outcome variables

For PFS, the proportion of patients who are progression-free at 24 weeks will be calculated for each treatment group. Non-inferiority of the 12-weekly ZOLADEX 10.8 mg treatment regimen to the 4-weekly ZOLADEX 3.6 mg regimen will be concluded if the lower limit of the 95% CI for the difference (10.8 mg minus 3.6 mg) is above -17.5%. The CI for this difference will be calculated using the score-based method recommended by Newcombe et al 2000.

The choice of this limit is based on a 75% relative efficacy of the 12-weekly ZOLADEX 10.8 mg treatment to the 4-weekly ZOLADEX 3.6 mg regimen, for which a 24-week progression-free proportion of 70% is anticipated.

In the analysis, a subject whose overall response at Visit 4(Week 24) is missing or NE will be treated as non-progression-free subject. Though the time window for Visit 4 is set as 24 weeks+7days (see Table 2), a tumour assessment performed 25 weeks or later will be handled as the assessment at Visit 4. However, in case that the tumour assessment for Visit 4 is performed 23 weeks or earlier, the overall response at Visit 4 will be handled as missing.

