12.2.5 Interim analysis -NA

12.3 Determination of sample size

In a study by Klijn et al 2001 and the trial 0008, the proportion of patients who had not progressed during the first 6 months (24 weeks) of treatment with the combination of ZOLADEX 3.6 mg and tamoxifen was estimated to be approximately 70%. Assuming the proportion of patients who are progression-free at 24 weeks is 70% in both treatment groups in this study (and therefore that there is no underlying difference between the two treatment regimens), and define the limit of non inferiority as an absolute difference of 17.5% between these two proportions, a sample size of 216 patients (108 per group) ensures that 80% power is achieved to conclude non inferiority with a two-sided 95% CI (or in other words, at the one-sided 2.5% level of statistical significance). The non inferiority limit of 17.5% equates to the 12 weekly ZOLADEX 10.8 mg regimen having at least 75% of the efficacy of the 4 weekly ZOLADEX 3.6 mg regimen.

The study will also collect PK (and additional E₂) data from a subgroup of patients allocated to the ZOLADEX 10.8 mg treatment group. It is planned to have at least 20 patients with evaluable PK data for this subgroup (at least 10 Japanese patients from Japan, and at least 10 Non Japanese patients from non-Japanese countries except for China). The sample size for this subgroup is not based on formal sample size considerations. Recruitment to this subgroup will be on an ongoing basis until the required number of patients with evaluable PK data are enrolled. Patient recruitment to the main study may be increased above the planned 216 evaluable patients in order to ensure 10 Japanese and 10 Non Japanese patients with evaluable PK data.

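### Prior first-line chemotherapy for advanced disease is recorded but used only in an optional exploratory analysis; adjusting the primary difference for it would be a small, nearly free gain in precision

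*Protocol*

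**What the plan says.** - **Eligibility.** Exclusion 6 in Protocol Section 4.2 rules out chemotherapy for advanced breast cancer "with the exception of first line chemotherapy providing that" there was no progression since it started and the patient had menses after starting it. The trial therefore mixes patients with and without such treatment.
- **Data.** Section 6.2.1 records "Previous therapy, including surgery for early breast cancer" at screening, and exclusion 6 cannot be checked without the chemotherapy history.
- **Randomisation.** Section 5.2.1 randomises per centre. Prior chemotherapy is not a stratum.
- **Primary analysis.** Section 12.2.1.1 takes the difference in the proportions progression-free at 24 weeks (10.8 mg minus 3.6 mg). "The CI for this difference will be calculated using the score-based method" attributed there to Newcombe. No covariate or stratum is named.
- **Use of the factor.** Section 12.2.1.2 says: "Exploratory analyses may investigate whether there is any additional effect of prior chemotherapy" for advanced disease on efficacy and/or PD outcomes. It is the one patient characteristic that section singles out for a possible look at efficacy. The same section adjusts the secondary oestradiol comparison for baseline value and country, but not for prior chemotherapy.

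**The concern.** If the two chemotherapy histories carry different 24-week progression risks, part of the variation in the unadjusted difference comes from how many patients of each kind fall in each arm. A stratified estimate removes that part with data already collected. The plan has little power in reserve: 80%, with no inflation for dropout stated in Section 12.3, and with missing or non-evaluable Week 24 responses counted as failures in Section 12.2.1.1. A modest gain is therefore worth having if it costs almost nothing.

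Timing is the second reason to name the adjustment now. The trial is open label, and Section 12 requires the SAP only before database lock. An adjusted estimate first chosen late in the trial would carry less weight for a non-inferiority claim than one named in the protocol.

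**Working it through.** **Inputs from the protocol**
- Section 12.2: "All confidence intervals (CIs) will be two-sided, 95% intervals"; Section 12.3 equates this to testing "at the one-sided 2.5% level of statistical significance".
- Section 12.3: "Assuming the proportion of patients who are progression-free at 24 weeks is 70% in both treatment groups in this study"; margin 17.5 points; "a sample size of 216 patients (108 per group) ensures that 80% power is achieved".

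**The plan's own figure**

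n per arm = 2 x 0.7 x 0.3 x (1.960 + 0.842)^2 / 0.175^2 = 0.42 x 7.849 / 0.030625 = 107.6, rounded up to 108, or 216 in total. This reproduces the stated size, which already assumes an unadjusted analysis.

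At 108 per arm:
- SE = sqrt(0.42/108) = 0.0624
- 95% half-width = 1.96 x 0.0624 = 12.2 points
- power = Phi(0.175/0.0624 - 1.96) = 80.1%

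**Inputs that must be assumed**

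The protocol gives neither the share f of patients with prior first-line chemotherapy for advanced disease nor the difference d in progression-free proportion between the two histories. I take f from 20% to 50% and d from 0 to 25 points in either direction, with the overall proportion held at 70%. The central case is f = 40%, d = 15 points.

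**Formulas**
- Share of variance removed by stratifying: R = f(1-f)d^2 / 0.21
- Power after adjustment: Phi(0.175 / (SE x sqrt(1-R)) - 1.96)
- Extra patients giving the same precision without adjustment: 216/(1-R) - 216
- 95% limit of the shift in the unadjusted difference from chance imbalance: 1.96 x d x sqrt(2f(1-f)/108)

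For the central case, R = 0.4 x 0.6 x 0.0225 / 0.21 = 0.0054/0.21 = 2.6%.

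| f | d (points) | Variance removed | Half-width (points) | Power | Equivalent extra patients | Imbalance shift, 95% limit (points) |
|---|---|---|---|---|---|---|
| any | 0 | 0% | 12.2 | 80.1% | 0 | 0 |
| 20% | 10 | 0.8% | 12.2 | 80.4% | 2 | 1.1 |
| 30% | 15 | 2.3% | 12.1 | 81.0% | 5 | 1.8 |
| 40% | 15 | 2.6% | 12.1 | 81.1% | 6 | 2.0 |
| 40% | 20 | 4.6% | 11.9 | 81.9% | 10 | 2.6 |
| 50% | 25 | 7.4% | 11.8 | 83.1% | 17 | 3.3 |

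A more extreme assumption, f = 50% and d = 30 points, gives 10.7% and 84.4%.

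**Is the imbalance shift extra error?** No. In the central case, sqrt(12.06^2 + 1.96^2) = 12.22, which is the unadjusted half-width. The shift is one component of an interval that already allows for it.

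The imbalance formula treats allocation as simple randomisation with respect to the factor. If chemotherapy history differs by centre, per-centre blocks would balance it in part, and both the shift and the gain would be smaller.

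**The case against.** The strongest case against is that nothing here is an error. A difference in two proportions with a score interval is a valid primary analysis of a randomised trial, is simple, and is the analysis on which the sample size rests. That stands.

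Three stronger readings are tempting, and the protocol does not support them.

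- **That the protocol expects prior chemotherapy to affect outcome.** Section 12.2.1.2 asks only whether there is an effect. No section says that the factor is prognostic, how common it is or in which direction it acts. Exclusion 6 admits only patients without progression on that chemotherapy, and Section 12.2.1.2 notes that some may be in complete remission, so even the direction is unclear.
- **That chance imbalance threatens the non-inferiority conclusion beyond what the interval shows.** The unadjusted interval covers it on average over randomisations, as the working shows. Only protection in the particular sample is lost.
- **That any look at the factor would be post hoc.** The protocol already names it in advance, and the SAP due before database lock may specify the analysis.

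Two further objections carry some weight. The central gain of about one power point is smaller than the gap between normal-approximation power (80.1%) and the exact power of the Newcombe-type score interval at 108 per arm (81.4%). Other recorded or eligible characteristics, such as HER2 status, progesterone receptor status and performance status, could also be candidates, as could centre. The reason to prefer prior chemotherapy is only that the protocol itself singles it out. The SAP could add an adjusted sensitivity analysis, but the primary method is fixed in protocol text, so a change to it belongs there.

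**Conclusion.** The point holds as a low-severity improvement. The primary analysis is valid but leaves unused a baseline factor that is allowed, recorded, not a randomisation stratum, and picked out by the protocol for a possible efficacy look. Under the assumed ranges, adjustment removes 0-7.4% of the variance and takes power from 80.1% to between 80.1% and 83.1%; the central case gives 2.6% and about 81.1%, worth about 6 patients. If the factor is not prognostic, nothing is gained.

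A reader might infer that the unadjusted analysis is biased or that its type I error is at risk because of this factor. Neither follows. These sizes rest on assumed prevalence and effect, not on figures in the protocol.

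**What to change.** In Section 12.2.1.1, name one primary estimator: the Mantel-Haenszel risk difference in 24-week progression-free proportions, stratified by prior first-line chemotherapy for advanced disease (yes/no), with a stratified score-type 95% interval. Compare its lower limit with the same -17.5% margin, which remains on the absolute difference scale. Keep the unadjusted Newcombe interval as a stated sensitivity analysis. Make the matching change in Section 12.2.1.2, so that the factor's role in the primary outcome no longer depends on an optional analysis.

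The cost is a change of protocol wording, made before outcome data by arm are reviewed, and a few lines of programming. It needs no new data and no additional patients, and the stated sample size can stay as it is.

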12.2.2 Analysis of safety outcome variables (main study)

12.2.2.1 Adverse events

AEs will be classified by MedDRA preferred term (PT) and system organ class (SOC).

All data on AEs that occurred after obtaining informed consent will be listed. AEs that occurred after administration of the investigational product will be summarised by treatment group, SOC, PT and the worst Grade of CTCAE v3.0. Drug related adverse events data will also be summarised in the same manner.

Individual patient data on all SAEs, deaths and AEs leading to discontinuation of the study as well as all AEs assessed, as OAEs will be listed.

12.2.2.2 Clinical laboratory data

Clinical laboratory data will be listed at each observation point and summarised by treatment group using descriptive statistics (n, mean, sd, median, min and max). The listing will also present deviations from the reference ranges established by AstraZeneca. Also graphs of laboratory data will be prepared.

12.2.2.3 Vital signs

Data on vital signs will be listed for each time point and summarised by treatment group using descriptive statistics.

12.2.3 Analysis of the pharmacokinetic subgroup

Analyses of PK outcomes will be performed on samples provided by patients in the PK subgroup set (all of whom received ZOLADEX 10.8 mg).

The plasma concentration–time profiles of goserelin in Japanese and Non Japanese(except for China) patients will be evaluated. From the individual plasma concentration–time profiles of goserelin following the first dose of ZOLADEX 10.8 mg, the following parameters will be derived and analysed using descriptive statistics: C_{max} , T_{max} , $AUC_{(0-t)}$, and $AUC_{(0-12 \text{ weeks})}$.

The E_2 concentration-time profiles will also be investigated in the PK subgroup using the E_2 subgroup set. If the data allows, the relationship between goserelin plasma concentrations and E_2 suppression may be investigated, as appropriate.

12.2.4 Testing for treatment-country interaction

For the PFS at 24 weeks and the ORR, Breslow-Day test with a 5% level will be performed to assess homogeneities across countries.

12.2.5 Interim analysis -NA

12.3 Determination of sample size

In a study by Klijn et al 2001 and the trial 0008, the proportion of patients who had not progressed during the first 6 months (24 weeks) of treatment with the combination of ZOLADEX 3.6 mg and tamoxifen was estimated to be approximately 70%. Assuming the proportion of patients who are progression-free at 24 weeks is 70% in both treatment groups in this study (and therefore that there is no underlying difference between the two treatment regimens), and define the limit of non inferiority as an absolute difference of 17.5% between these two proportions, a sample size of 216 patients (108 per group) ensures that 80% power is achieved to conclude non inferiority with a two-sided 95% CI (or in other words, at the one-sided 2.5% level of statistical significance). The non inferiority limit of 17.5% equates to the 12 weekly ZOLADEX 10.8 mg regimen having at least 75% of the efficacy of the 4 weekly ZOLADEX 3.6 mg regimen.

The study will also collect PK (and additional E₂) data from a subgroup of patients allocated to the ZOLADEX 10.8 mg treatment group. It is planned to have at least 20 patients with evaluable PK data for this subgroup (at least 10 Japanese patients from Japan, and at least 10 Non Japanese patients from non-Japanese countries except for China). The sample size for this subgroup is not based on formal sample size considerations. Recruitment to this subgroup will be on an ongoing basis until the required number of patients with evaluable PK data are enrolled. Patient recruitment to the main study may be increased above the planned 216 evaluable patients in order to ensure 10 Japanese and 10 Non Japanese patients with evaluable PK data.

12.4 Data monitoring committee – NA

13. IMPORTANT MEDICAL PROCEDURES TO BE FOLLOWED BY THE INVESTIGATOR

13.1 Medical emergencies and AstraZeneca contacts

The Principal Investigator is responsible for ensuring that procedures and expertise are available to handle medical emergencies during the study. **A medical emergency usually constitutes an SAE and is to be reported as such, see Section 6.4.4**

In the case of a medical emergency the investigator(s) may contact the Study Delivery Team Leader. If the Study Delivery Team Leader is not available, contact the Study Delivery Team Physician

Name	Role in the study	Address & telephone number

13.2 Overdose

- An overdose with associated AEs is recorded as the AE diagnosis/symptoms on the relevant AE modules in the eCRF and on the Overdose eCRF module.
- An overdose without associated symptoms is only reported on the Overdose eCRF module.

There is limited experience of ZOLADEX overdose in humans. In cases where ZOLADEX has unintentionally been re-administered early or given at a higher dose, no clinically relevant adverse effects have been seen. Animal tests suggest that no effect other than the intended therapeutic effects on sex hormone concentrations and on the reproductive tract will be evident with higher doses of ZOLADEX. If overdose occurs, this should be managed symptomatically.

Theoretically, overdosage of tamoxifen in humans might cause enhancement of the pharmacological side effects associated with its usage (eg, hot flushes, vaginal bleeding,

vaginal discharge, pruritus vulvae and tumour flare). There have been reports in the literature that tamoxifen given at several times the standard dose may be associated with prolongation of the QT interval of the electrocardiogram. Observations in animals show that extreme overdosage (100 to 200 times the recommended daily dose) may produce oestrogenic effects. There is no specific antidote to overdosage with tamoxifen and treatment must be symptomatic.

In this study, the following constitutes an overdose of study medication:

- >40 mg of tamoxifen in a one day period
- >1 ZOLADEX 3.6 mg injection in a 3-week period, or
- >1 ZOLADEX 10.8 mg injection in an 11-week period

Use of study medication in doses in excess of that specified above should not be recorded in the eCRF as an AE of 'Overdose' unless there are associated symptoms or signs.

An overdose with associated SAEs should be recorded as the SAE diagnosis/symptoms on the relevant SAE forms in the eCRF. Investigators must inform the sponsor of any SAEs within 24 hours of being aware of the SAE (see Section 6.4.4 for reporting of SAEs).

An overdose with associated non-serious AEs should be recorded as the AE diagnosis/symptoms on the relevant AE forms in the eCRF. In addition, the overdose should be reported on a separate clinical study overdose report form, which will be sent to the sponsor.

An overdose without associated symptoms should not be recorded as an AE in the eCRF. The overdose should be reported on a separate clinical study overdose report form, which will be sent to the sponsor.

